4.0 NUMBER OF PARTICIPANTS

A total of 100 participants will be recruited:

Protocol ShapeNZRCT-10 and ShapeNZEx-13_Final_v4_25Mar2014_Clean

 50 cases will be performed using the Stryker ShapeMatch[®] Cutting Guides to achieve kinematic alignment (Intervention Group).

 50 cases will be performed using computer-assisted Navigation and conventional instruments to achieve neutral mechanical axis alignment (Control Group).

Extension study: Patients from both the intervention and the control groups will be invited; a maximum of 100 patients will be included.

5.0 LENGTH OF STUDY AND PATIENT PARTICIPATION

The enrolment period is expected to be 6 months or until the required sample size is reached. Participants in both the Control Group and Intervention Group will be followed for 12 months post-surgery. It is anticipated that the entire study will take approximately 18 months to complete, excluding data analysis.

Following the 12 month follow-up visit, patients will receive an invite to continue participation in the study via enrollment into the Extension Study. Patients will need to meet the inclusion and exclusion criteria for the study (see sections 6.3 and 6.4) and provide informed consent in order to participate.

6.0 PATIENT SELECTION CRITERIA

Each Investigator is responsible for evaluating each patient against the following criteria and assuring that the patient meets the requirements to be enrolled in this clinical investigation. Each patient enrolled in this investigation must meet each of the following inclusion criteria and have none of the exclusion criteria. Any patient enrolled in this study who does not meet the inclusion and exclusion criteria will be considered a protocol deviation.

6.1 Inclusion Criteria

- The patient is a male or non-pregnant female between the ages of 40-80 years.
- The patient requires a primary total knee replacement and is indicated for computer-assisted surgery.

- Patient is deemed appropriate for a cruciate retaining knee replacement.
- The patient has a primary diagnosis of osteoarthritis (OA).
- The patient has intact collateral ligaments.
- The patient is able to undergo MRI scanning of the affected limb.
- The patient has signed the study specific, ethics-approved, Informed Consent document.
- The patient is willing and able to comply with the specified pre-operative and post-operative clinical and radiographic evaluations.

6.2 Exclusion Criteria

- The patient has a history of total, unicompartmental reconstruction or fusion of the affected joint.
- Patient has had a previous osteotomy around the knee.
- The patient is morbidly obese (BMI ≥ 40).
- The patient has a deformity which will require the use of stems, wedges or augments in conjunction with the Triathlon Total Knee System.
- The patient has a varus/valgus malalignment ≥ 15° (relative to mechanical axis).
- The patient has a fixed flexion deformity ≥ 15°.
- The patient has a neuromuscular or neurosensory deficiency, which would limit the ability to assess the performance of the device.
- The patient has a systemic or metabolic disorder leading to progressive bone deterioration.
- The patient is immunologically suppressed or receiving steroids in excess of normal physiological requirements.
- Patient has a cognitive impairment, an intellectual disability or a mental illness.
- The patient is pregnant.
- The patient has metal hardware present in the region of the hip, knee or ankle (as this is known to create geometrical distortion in the region of the implant).
- The patient has any known contraindications for undergoing assessment by MRI (e.g. ferrous implants, metallic clips, magnetically activated implanted devices such as cardiac pacemakers, etc.).

6.3 Extension Study: Inclusion Criteria (applicable to patients electing to continue participation in the Extension Study)

- Patient was enrolled in ShapeNZRCT-10 and completed either the 6 month or 12 month follow-up visit (or both).
- Patient is willing and able to give informed consent to participate in the study.
- Patient is willing and able to comply with the specified clinical and radiographic evaluations.

6.4Extension Study: Exclusion Criteria (applicable to patients electing to continue participation in the Extension Study)

- Patient no longer has the Triathlon[®] Total Knee System in situ, including patients that have had revision surgery.
- Patient has a cognitive impairment, an intellectual disability or a mental illness that is considered by the investigator to inhibit the patient's capacity to consent to research and the ability to participate in it.
- Patient no longer resides in a geographical location that would reasonably permit clinic visits at protocol specified intervals.

7.0 STUDY DESIGN

This study will be conducted as a randomised controlled trial, designed to limit confounding bias. Participants will be recruited and assessed against the Inclusion and Exclusion criteria. If participants met these criteria they will be randomised to either the Control Group or the Intervention Group, with no other factors of influence.

This will be achieved via a block randomisation process. A central randomisation list will be computer generated by a consultant statistician. Once a patient has met criteria for enrolment, the Principal Investigator or designee will phone/email the Sponsor with the Initials, Date of Birth and Patient Number (assigned in ascending order at time of recruitment). A randomisation number, corresponding to a randomisation envelope held at the study site, will be provided. Once this number is received the envelope will be located and opened. The Principal Investigator will note the group allocation in the Case Report Form.

Patients will be blinded to their group allocation. This will allow minimal bias when completing post-operative questionnaires.

Pre- and post-operative x-rays will also be reviewed by a blinded reviewer.

Control Group - Neutral Mechanical Alignment using Navigation

Participants randomised to the Control Group will undergo Total Knee Replacement (TKR) with the goal of neutral alignment to the mechanical axis. This is the standard method for TKR with Triathlon[®] Knee System and this group will serve as a control reference for the intervention group.

Intervention Group - Kinematic Alignment using ShapeMatch®

Participants randomised to the Intervention Group will undergo TKR with the goal of kinematic alignment, re-aligning the limb to its pre-disease kinetic alignment.

Both groups will undergo treatment in parallel. The study will be conducted as a two-centre study with approximately 7 surgeons performing surgery for this study.

Patients will be followed up until 12 months post-surgery and those participating in the extension study will be followed until 5 years post-surgery.

8.0 DEVICE DESCRIPTION

8.1 Device Trade Name

The prosthetic components to be implanted as part of this study in both the Control Group and the Interventional Group include:

- Triathlon[®] Cruciate Retaining (CR) Total Knee System (cemented), including Femoral Component and Primary Tibial Baseplate;
- Triathlon® Cruciate Substituting (CS) X3® polyethylene insert;
- Triathlon[®] X3 Patella (asymmetric) treated selectively by surgeon.

The instruments used to resect the distal femur and proximal tibia as part of this study will differ between the Control Group and Intervention Group. The instruments used

Protocol ShapeNZRCT-10 and ShapeNZEx-13_Final_v4_25Mar2014_Clean

in the Control Group will be the conventional, approved instruments used with the above listed Triathlon® products.

The instruments used in the Interventional Group will be the approved ShapeMatch® Cutting Guide (including Femoral and Tibial cutting guides). These devices are single-use, patient-specific instruments.

The above named products are commercially available, MedSafe NZ listed devices (notified on the NZ WAND Database), and are approved for sale and use throughout New Zealand.

In addition, the Stryker PrecisioN Knee (4.0) Navigation System, comprising of computer hardware and software and associated instrumentation, will be used for intra-operative alignment and orientation of implant in the Control group. This system is also a commercially available, MedSafe listed device, and approved for sale and use throughout New Zealand.

8.2 Device Supply

The ShapeMatch[®] cutting guides will be supplied by Stryker New Zealand Ltd.

All other devices used in this study are commercially available products which will be obtained via the usual ordering and payment process.

9.0 SURGICAL PROCEDURES

Control Group: Each patient will be prepared to undergo a primary total knee replacement using the Triathlon Primary Total Knee System and Stryker PrecisioN Knee Navigation System. A standard skin incision and joint exposure will be performed according to the surgeon's preference. Navigation trackers will be secured to the femur and tibia and registration of the limb will be undertaken according to the PrecisioN Knee System surgical technique.

Femoral and tibial resections, followed by device implantation, will be performed according to the Triathlon Knee System Surgical Protocol.

Appropriate post-operative care will be provided according to the preference of the treating physician. Post-operative assessments will be undertaken according to the study protocol.

Intervention Group: Each patient will be prepared to undergo a primary total knee replacement using the Triathlon Primary Total Knee System, implemented using Stryker OtisMed[®] ShapeMatch[®] Technology. A standard skin incision and joint exposure will be performed according to the surgeon's preference.

The appropriate Stryker ShapeMatch[®] Cutting Guide will be positioned onto the distal femur, and secured in place using fixation pins. The distal femoral bone resection will be completed and the block removed. Completion of the bone preparation of the distal femur will be undertaken using manual instruments.

The same procedure will be performed on the proximal tibia using the appropriate Stryker ShapeMatch® Cutting Guide.

The surgeon will implant the knee prostheses following the surgical protocol for Triathlon[®] Knee System with OtisMed[®] ShapeMatch[®] Technology (Appendix 1).

Appropriate post-operative care will be provided according to the preference of the treating physician. Post-operative assessments will be undertaken according to the study protocol.

10.0 INFORMED CONSENT

The Investigator will inform potential study candidates of the purpose of the study, proposed duration of the study, including the study-specific procedures and evaluations. The Investigator will discuss foreseeable risks involved, as well as potential benefits that may result for future participants through the outcomes of this study. Following this verbal discussion with the Investigator, participants will then be given time to read, understand, and, if agreeable, sign the study-specific Participant Consent Form indicating their agreement to participate in the study.

De-identified patient information will be used during the analysis of the results of the clinical study and the confidentiality of the participants will be maintained at all times. Patient records will be stored with the surgeon's normal secure record storage system.

The participants will be informed by the Investigator that they are free to refuse participation in this Investigation, and if they decline or withdraw from the study at any time this will not compromise further medical care.

A signed and dated Participant Consent Form must be obtained by the Investigator from the patient prior to enrolment into this study. The original signed and dated Patient Information Sheet and Consent Form will be kept by the Investigator. A copy will be provided to the patient, and another copy placed in the patient's hospital medical record.

Should a patient undergo any study procedure without signing a Participant Information and Consent Form, the Investigator must notify the applicable Ethics Committee and study Sponsor of the deviation, detailing the circumstances which resulted in the failure to obtain informed consent. The Investigator will then follow Ethics Committee instructions on how to handle patient/situation and obtaining consent.

Patients willing to participate in the extension study will undergo a second informed consent process with a new patient information sheet detailing the additional study-specific procedures. This process will be carried out in the same manner as the original informed consent process.

11.0 EVALUATIONS

All data will be recorded on the Case Report Forms. The designated signatory (e.g. Investigator, delegated authority, participant, etc.) will complete and sign forms at the time of each required visit specified by the study protocol.

All participants will have detailed information collected pre- and post-operatively as part of their involvement in this study. Participants will be assessed at 6 weeks, 6 months and 12 months after surgery.

The following data will be captured throughout the study:

Patient Demographics: A record of the patient's date of birth, gender, height, weight, and medical history will be obtained pre-operatively and reviewed again for the Extension Study.

Surgical Details: A summary of the surgical procedure will be collected during the operation. This will include details of the prosthetic components implanted, operating time and comments. Data relating to the number of instruments sterilized and used during each surgical case will be collected. Parameters relating to the effect of each instrumentation platform on costs and efficiency within the hospital environment will also be assessed. These details will be reviewed again for those patients continuing into the Extension study.

Medical Imaging (and Extension Study participants):

Standard Anterior-Posterior (AP) and Medio-Lateral (ML) X-rays of the affected limb will be obtained pre-operatively and post-operatively to assess implant stability.

Extension Study participants will undergo **two Long Leg AP** weight bearing x-rays to evaluate alignment of the limb; one at 2 years and 5 years post-surgery.

An MRI scan according to the OtisMed Imaging Technique will be undertaken preoperatively to obtain detailed three-dimensional detail of the affected knee and will be transferred to Stryker OtisMed, Alameda CA for development of customized cutting guides. To maintain blinding of participants, both the Control Group and the Interventional Group will undergo MRI scanning.

A CT scan will be obtained 3 months after surgery according to the Perth CT protocol. A published technique will also be undertaken to obtain detailed three-dimensional descriptions of the position and orientation of the implanted components (Appendix 3;

Chauhan et al., 2004). Limb alignment and TKR component position will be compared to the alignment goal for patients in each of the two groups.

Patient outcome measurements (see Appendix 4):

Oxford Knee Score: A patient-completed 12-item questionnaire, designed specifically for patients undergoing total knee replacement. Each of the 12 items has 5 scoring categories. It is short, practical, reliable, valid and sensitive to clinically important changes over time (Dawson et al, 1998).

The International Knee Society System (IKSS): a universally-accepted tool for assessment of TKR clinical and functional outcomes. It separates findings in the operated knee with findings in the patient's function. As such the Knee Score is not artificially affected by co-morbid conditions. The Knee Score consists of points given for pain, range of motion, and stability in both the coronal and sagittal planes, with deductions for fixed deformity, and extensor lag. The Function Score consists of points given for the ability to walk on level surfaces, and the ability to ascend and descend stairs, with deductions for the use of external supporting devices (Insall et al., 1990).

FJS-12: The Forgotten Joint Score is a newly-developed twelve-item, self-reported assessment of how aware recipients of hip and knee joint replacement are of their joint in everyday life (Behrend et al., 2010).

WOMAC: The Western Ontario and McMaster Universities Arthritis Index is a set of standardised self-administered questionnaires used to evaluate the condition of patients with osteoarthritis of the hip and knee. It assesses the pain, joint stiffness, physical, social and emotional function of a person with osteoarthritis. A reduced version of WOMAC has been validated and published by Whitehouse et al (2003) and will be used in this study.

Euro-Qol (EQ-5D-3L): The EQ-5D-3L is a standardised patient-completed instrument for use as a measure of health outcome (Fransen and Edmonds, 1999). It consists of dimensions: mobility, self-care, usual activities, pain/discomfort, and

anxiety/depression. There are 3 levels of severity to select from within each dimension.

VAS Pain: A graphic Visual Analogue Scale (VAS) used as measurement instrument for patients to indicate their level of pain. The amount of pain that a patient feels is believed to range across a continuum from none to an extreme amount of pain i.e. from the patient's perspective this spectrum appears continuous - their pain does not take discrete jumps, as a categorization of none, mild, moderate and severe (Wewers et al., 1990).

Medical History Review: For participants continuing on in the extension study, details of any significant medical events that occur from the end of the 12 month study period to the signing of the extension study consent form will be captured as medical history in the extension study. This will ensure no adverse event data will be missed between termination from the ShapeNZRCT-10 study and re-enrolment into the Extension study.

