3.0 OBJECTIVES

The primary objective of this study is:

• To demonstrate, through calculation of Oxford Knee Score at 12 months postoperative, that total knee replacement (TKR) performed using the ShapeMatch® Cutting Guide provides improvement from preoperative levels of patient pain and function comparable to the improvement obtained with TKR performed using computer-assisted Navigation. Oxford Knee Scores will be calculated pre-operatively and at 6 weeks, 6 months and 12 months post-operatively.

The secondary objectives of this study are:

- The efficacy objective is to compare radiographic, pain, function and health-related quality of life (QOL) between the ShapeMatch® Cutting Guide group and the computer-assisted Navigation control group. This objective will be achieved by utilizing the following instruments pre-operatively and at the 6-week, 6-month and 12 month visits:
 - Perth CT protocol
 - AP and ML X-rays
 - Oxford Knee Score
 - The International Knee Society Score (IKSS)

- The Forgotten Joint Score (FJS-12)
- WOMAC
- EQ-5D-3L
- VAS Pain
- To compare the cost-effectiveness and cost-utility of the procedure between the ShapeMatch[®] Cutting Guide group and the computer-assisted Navigation control group. This objective will be assessed by recording and calculating the following parameters:
 - o Wound length
 - Total duration of operating procedure (anaesthetic time and skinto-skin incision time)
 - o Cost of consumable items used during operating procedure
 - Length of stay in hospital
 - o Quality-adjusted life-years (QALYs) from EQ-5D-3L

The hypothesis is that there is a statistically significant improvement in functional outcome 12 months following a primary Total Knee Replacement when kinematic limb alignment (using ShapeMatch® Cutting Guide) is used compared to that resulting from a goal of neutral mechanical axis alignment (using computer-assisted Navigation).

The Extension Study Primary Objective is:

To determine the clinical and radiographic outcomes at 2 years and 5 years post-surgery, in patients receiving a Stryker Triathlon[®] Total Knee System for Total Knee Arthroplasty (TKA) implanted using either Stryker OtisMed[®] ShapeMatch[®] Technology (intervention) or Stryker PrecisioN v4.0 Knee Navigation (control).

The Extension Study Secondary Objectives are:

 To determine the revision rate, device-related adverse events and reoperation rates.

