19.2 Reporting of Events

Adverse Events:

Any adverse event that occurs at any time point from the beginning of the surgical procedure until either the patient is terminated from the study, or 30 days post-completion, should be recorded as follows:

All information on general medical, operative and device related complications (adverse events) will be documented on Case Report Forms (CRFs). Information should include date of occurrence, description, severity, relationship to study device, treatment and date of resolution.

The Investigator must determine if the event is related to the device. Any adverse event in a study patient must be monitored until the event is resolved or considered non-clinically significant by the Investigator.

Expected Events: Should be reported to the Sponsor soon as possible, but not later than ten working days after the Investigator first learns of the effect.

Adverse Device Events

Should any adverse device events occur, the study staff will ensure that these are documented by the Investigator and reported immediately to the Sponsor. They should also be reported to the reviewing Ethics Committee and Institution as soon as possible, but not later than fifteen working days after the Investigator first learns of the effect, unless an earlier timeline is specified by individual study sites. The Investigator with the Sponsor will conduct an evaluation of such effects. Following this evaluation, if the Investigator determines that an unanticipated adverse device effect presents an unreasonable risk to participants, the Investigation will be terminated as soon as possible. Termination shall occur no later than five working days after the Investigator makes this determination and no later than fifteen working days after the Investigator first receives notice of the unanticipated adverse effect.

Serious Adverse Events:

Any adverse event that is considered to be of serious nature and occurs at any time point from the signing of Informed Consent Form until either the patient is terminated from the study, or 30 days post-completion, should be recorded as follows:

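### The rule for events between the 12-month trial and Extension consent does not deliver its assurance that no adverse event data are missed, so Extension event rates may be understated

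*Combined protocol and SAP*

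**What the plan says.** Section 11.0 (Medical History Review) bridges the two studies. Its scope is: "For participants continuing on in the extension study, details of any significant medical events that occur". The period and the type of record follow: "from the end of the 12 month study period to the signing of the extension study consent form will be captured as medical history". It then gives an assurance: "This will ensure no adverse event data will be missed between termination from the ShapeNZRCT-10 study and re-enrolment into the Extension study".

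Section 19.2 governs adverse events proper. Both the general adverse event paragraph and the serious adverse event (SAE) paragraph apply "until either the patient is terminated from the study, or 30 days post-completion, should be recorded as follows". For each adverse event, "Information should include date of occurrence, description, severity, relationship to study device, treatment and date of resolution". The paragraph on adverse device events states no end date, and its ethics committee clock runs from when the investigator learns of the effect.

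Three other places matter:

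- Section 6.3 admits to the Extension a patient who "completed either the 6 month or 12 month follow-up visit (or both").
- Section 5.0 places the invitation after month 12 but sets no latest date for consent: "Following the 12 month follow-up visit, patients will receive an invite to continue participation in the study".
- Section 3.0 gives the Extension secondary objective: "To determine the revision rate, device-related adverse events and reoperation rates".

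Section 12.2 tabulates adverse events. It does not say how interval events held as medical history are treated.

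**The concern.** The assurance and the rule beside it do not match. The assurance speaks of all adverse event data, counted from termination. The rule takes only events judged significant (a term the plan does not define), counts from the end of the 12-month period, and files them in a record for which no adverse event fields are named.

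At stake is the Extension safety objective. An event with no recorded judgement on device relationship cannot be placed in or out of a count of device-related adverse events, and that judgement is hard to reconstruct years later.

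The patients who can fall between the two records are not a random subset. Section 17.2 lists re-operation of the study knee as a reason for not continuing, and section 17.3 terminates unblinded patients. A patient re-operated on after the 6-month visit with the implant still in place can leave the trial and still qualify for the Extension. The re-operation itself would be recorded, but a later complication before month 12 might not be.

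**Working it through.** The plan states no adverse event or re-operation rate, so there is no figure of its own to reproduce. The check sets the recording periods side by side and measures the intervals.

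**1. Content of the two records.** Section 19.2 names date, description, severity, device relationship, treatment and resolution. Section 11.0 asks for details of significant events and names no fields. Severity and device relationship are therefore not required for interval events.

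**2. Patients who complete 12 months.** Inputs: completion at month 12 (section 1.0), plus 30 days, taken as 1 month (section 19.2), so adverse event recording ends at about month 13. The 2-year window is 24 ± 6, that is months 18 to 30 (section 1.0). The consent month c is not given, so it is an assumption and is varied. Time covered only by medical history = max(0, c − 13). The share is taken of months 12 to 60, which is 48 months.

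| Consent month (assumed) | Medical history only | Share of 48 months |
|---|---|---|
| 13 or earlier | 0 months | 0% |
| 18 | 18 − 13 = 5 months | 10% |
| 24 | 24 − 13 = 11 months | 23% |
| 30 | 30 − 13 = 17 months | 35% |

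The 12-month visit window of ± 2 months moves the recording cut-off to between months 11 and 15, so each non-zero figure shifts by up to 2 months either way.

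**3. Patients terminated early.** Recording stops at termination, month t. Taking the end of the 12-month period as month 12 after surgery, the look-back opens at month 12. The time in neither record is 12 − t. For termination directly after the 6-month visit (window 5 to 7 months) this is 12 − 7 = 5 to 12 − 5 = 7 months, and less for later termination. It does not depend on the consent date. A patient who only missed the month-12 visit has a missed visit, is not terminated, and stays under adverse event recording.

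**4. Illustration with assumed event rates.** Take 100 Extension patients (the plan's maximum) and an assumed constant annual rate of 1% to 5%. Expected events over 48 months are 100 × 0.01 × 4 = 4 to 100 × 0.05 × 4 = 20. Events falling in the interval number 100 × rate × gap/12:

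- gap 0: none
- gap 11 months: 0.92 to 4.58
- gap 17 months: 1.42 to 7.08

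These would be lost only if medical-history entries are not counted. For early leavers, assuming 1 to 10 such patients and a 6-month hole, the expected number is 1 × 0.01 × 0.5 = 0.005 to 10 × 0.05 × 0.5 = 0.25.

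**The case against.** The strongest reply is that no bias has been shown. The plan defines no numerator, denominator or risk period for the Extension rates, and nowhere says that medical-history entries are left out. Section 11.0 states its purpose as preserving adverse event data, which points towards using them. If interval events are counted, or if the rates start at Extension consent, under-counting of interval events as a class disappears. This stands. A reader might infer that the rates are too low; the documents support only that they may be. They do set Extension outcomes at 2 and 5 years after surgery, which suggests time from surgery, but they do not define the rates that way.

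A reader might also infer that close to a year of events is simply unrecorded. That assumes consent at the 2-year visit, whereas section 5.0 allows it soon after month 12, when the gap is nil. Significant events are in any case recorded, and sections 1.0 and 11.0 plan a review of medical history and surgical details. A re-operation would very likely be found.

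A third inference is that serious device events found at Extension consent escape reporting. The text does not support it: the adverse device event paragraph has no time limit. The lapse concerns the general adverse event and SAE paragraphs.

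Finally, the early-leaver hole is narrow, and the assurance shows that coverage from termination was intended. The case report forms are not in the documents and may ask for more than section 11.0 does. Both points are fair. Neither makes the written rule deliver what it promises.

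**Conclusion.** The point holds as a mismatch between a stated rule and its stated assurance, and it should be corrected. Two defects rest on the text alone: interval events need no severity or device-relationship assessment and are limited to significant ones, and the literal start date leaves termination to month 12 uncovered for early-terminated patients admitted on the 6-month visit. Possible understatement of the Extension rates follows from these, but its size cannot be computed. The interval lengths for completers rest on the assumed consent month, and the event counts rest on assumed rates as well.

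The exclusion of revised patients (section 6.4) and the end of trial participation at re-operation (section 17.2) also bear on the revision and re-operation rates. They are separate matters, and the change below does not resolve them.

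**What to change.** Replace the Medical History Review paragraph in section 11.0 and add a sentence to section 12.2:

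- Start the look-back at each patient's actual adverse event cut-off: the termination date, or completion plus 30 days.
- At Extension consent, record all adverse events since that date on the existing adverse event form, with onset date, severity, seriousness, device relationship and outcome, flagged as retrospective.
- Report SAEs found this way from the site's first knowledge of them. Device events already follow their route in section 19.2.
- State that these events count in the Extension adverse event and re-operation tables, and define the risk period over which the rates are calculated.

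The cost is a short text change and some extra form completion at consent. Retrospective events will have less certain dates, and the flag allows a tabulation with and without them.
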